4.0 STUDY DESIGN

4.1 Overall Design

This is a proof-of-concept, randomised, double-blind, placebo-controlled, multi-centre study designed to evaluate the safety/tolerability and efficacy of 4 sc injections of namilumab 150 mg given over 10 weeks as therapy in subjects with moderately-to-severely active axSpA, including those with a history of inadequate response to or intolerance to anti-tumour necrosis factor (TNF) therapy. The study will allow enrolment of up to 50% of subjects with primary non-response to prior anti-TNF treatment.

The study will consist of a maximum 4-week Screening period, followed by a 12-week doubleblind treatment evaluation period, followed by a 16-week safety follow-up period, for a maximum study duration of approximately 32 weeks or 224 days per subject. Eligible subjects will be randomised on Day 1 of Week 0 and receive study treatment administered sc on Day 1 of Week 0, Week 2 (loading dose), Week 6 and Week 10. Subjects will return on Week 12 for an End of Treatment (EoT) visit during which efficacy and safety assessments will be performed. Subjects will have a follow-up visit 16 weeks after the EoT visit.

4.2 Scientific Rationale for Study Design

This study is designed as a phase 2a proof-of-concept study evaluation of namilumab in the treatment of subjects with axSpA. Subjects who have inadequately responded to or experienced intolerance to previous treatment with an anti-TNF agent may be included but will be limited to 50% of the total study population; this sub-population may respond significantly to namilumab, providing a sensitive basis for dose selection/optimisation in advance of further (phase 3) clinical development. The overall study population is also considered likely to benefit from the novel mechanism of namilumab, which may provide a new treatment option for subjects intolerant to or failing previous therapies.

The choice of 150 mg/mL namilumab for this investigation was based on the dose demonstrating maximal efficacy in clinical studies of rheumatoid arthritis and still within the margins of safety.

4.2.1 Subject Population Studied (Defined by Demography, Disease and/or Treatment Characteristics)

In order to ensure that the study data will be relevant to the future use of this agent in clinical practice, the design is representative of clinical practice in terms of both the selected study populations and concomitant medications (stable doses of NSAIDs, MTX, sulfasalazine or leflunomide).

4.2.2 Justification for Design and Sample Size

A parallel-arm, randomised, double-blind, placebo-controlled study design is a conventional and well-established design to assess proof-of-concept effects of new biologics in axSpA. This study design follows the Committee for Proprietary Medicinal Products (CPMP)/European Medicines Agency (EMA) Draft Guideline (12 October 2017): "*EMA Guideline on the Clinical Investigation of Medicinal Products for the Treatment of Axial Spondyloarthritis*" (EMA/CPMP/EWP/4891/03 Rev. 1).

Sample size justification is provided in Section 9.2.

4.2.3 Justification of Control Group

The choice and rationale of a control group is in accordance with the CPMP/EMA Guideline (December 2003). Section 5.1 of the guideline recommends use of placebo controls for a limited duration of 3 to 6 months. The use of NSAIDs with gastric protection and low-dose corticosteroids, all in stable doses, is allowed to ensure a minimum background treatment remains in place.

Acknowledging the general need to ensure use of a minimum period for treatment comparison with placebo in clinical studies, the planned investigation will be conducted over 12 weeks. Throughout this period discomfort for placebo-treated subjects will be minimised by the concomitant use of standard of care therapy: this approach will include stable dose pain-relief medication together which may include MTX.

4.2.4 Justification for Route, Dose Regimen, Treatment Period, with Reference to Previous Exposure, PK/PD Profile and Non-clinical Safety

This will be the first time that namilumab is to be administered subcutaneously to subjects with moderate-to-severe axSpA. Non-clinical studies have not revealed any risks associated with multiple dosing and clinical studies in healthy volunteers and subjects with RA and psoriasis have shown namilumab to be safe and well tolerated (see Investigator's Brochure). The current administration schedule is designed based on the simulation of pharmacokinetic (PK) results of the first-in-man study. With the selected schedule, the steady state serum concentration is expected to be reached by the second injection. The half-life of namilumab as determined from the first-in-man study data is 25 days and thus supports maintenance dosing with a 4-week interval.

The time to onset of action of namilumab in patients with axSpA is not established; however, it is expected to be in a range within 12 weeks from first administration. Therefore, some clinical effect is expected after 12 weeks in this study.

4.2.5 Justification for Primary Endpoints

The primary endpoint, Assessment in Ankylosing Spondylitis with 20% improvement (ASAS20) clinical response at 12 weeks, and the secondary endpoints, ASAS40, ASAS70, Ankylosing Spondylitis Disease Activity Score C-reactive Protein (ASDAS-CRP) response, and improvement of CRP, are consistent with the revised EMA Draft guidance (12 October 2017) for studies in axSpA.

4.3 Justification for Dose

The namilumab drug product is a single-dose liquid solution for sc injection containing 20 mg/mL, 50 mg/mL, 80 mg/mL or 150 mg/mL namilumab active ingredient. From the NEXUS study performed in subjects with moderate-to-severe RA, it was concluded that 150 mg was the most effective dose of namilumab in subjects with RA, as well as being associated with a manageable safety profile. In addition, the chronic toxicology study in cynomolgus monkeys demonstrated that the 150 mg dose in humans lies within a favourable therapeutic window of equivalent doses in monkeys (see Section 1.1.5 in the Investigator's Brochure). Therefore, the dose of 150 mg/mL was chosen for the current study in subjects with axSpA.

Treatment-related treatment-emergent AEs (TEAEs) associated with namilumab 150 mg were single cases of infection, oropharyngeal pain/dental caries, headache, decreases in neutrophil counts/neutropenia, elevated liver function tests and decreased forced expiratory volume (FEV)/force vital capacity (FVC) (see Table 6.b in the Investigator's Brochure). Based on haematology and clinical chemistry variables, there were no clinically significant or serious cases of neutropenia or abnormal liver function and there were no cases of confirmed PAP. No deaths or treatment-related SAEs were reported in subjects receiving namilumab 150 mg. These results suggest that the 150 mg dose chosen for the current study is safe and well tolerated.

4.4 End of Study Definition

A subject is considered to have completed the study if he/she has completed all phases of the study including the last visit.

The end of the study is defined as the date of the last visit of the last subject in the study.

5.0 STUDY POPULATION

Prospective approval of protocol deviations to recruitment and enrolment criteria, also known as protocol waivers or exemptions, is not permitted.

5.1 Inclusion Criteria

Subjects are eligible to be included in the study only if all of the following criteria apply:

- 1. Age ≥ 18 and ≤ 75 years of age.
- 2. Diagnosis of axSpA by an appropriately qualified physician and classified using ASAS criteria ≥3 months prior to Baseline; symptoms must have started before age 45.
- 3. Bath Ankylosing Spondylitis Disease Activity Index (BASDAI) score ≥4 and spinal pain score ≥40, at screening and Baseline.
- 4. MRI evidence of active axSpA ≤6 (ideally ≤3) months prior to randomisation using ASAS criteria.
- 5. A negative tuberculosis (TB) screening assessment.
- 6. A female subject of childbearing potential who is sexually active with a non-sterilised male partner agrees to routinely use adequate contraception from signing of the informed consent throughout the duration of the study until the end of the safety follow up (18 weeks after last dose) (see Appendix 7).
- 7. A male subject who is non-sterilised and sexually active with a female partner of childbearing potential agrees to use adequate contraception from signing of the informed consent throughout the duration of the study until the end of the safety follow up (18 weeks after last dose) (see Appendix 7).
- 8. Stable NSAID use for 28 days prior to study entry (see Appendix 5).
- Stable use of MTX (≤25 mg/week), sulfasalazine (≤3 g/day) or leflunomide (≤20 mg/day) for 28 days prior to study entry (see Appendix 5).
- 10. Stable oral corticosteroid dose ≤ 10 mg for 28 days prior to study entry (see Appendix 5).
- 11. Capable of giving signed informed consent as described in Appendix 2, which includes compliance with the requirements and restrictions listed in the informed consent form (ICF) and in this protocol.

In addition, the following inclusion criteria will apply for some subjects:

12. Inadequately responded to or experienced intolerance to previous treatment with an anti-TNF agent (limited to 50% of the total study population).

Note: Criteria for inadequate response to or experienced intolerance to previous treatment with an anti-TNF agent are defined as:

- Signs and symptoms of persistently active disease despite a history of at least one12week regimen of one of the following agents:
 - Infliximab: 5 mg/kg i.v.
 - Etanercept: 50 mg weekly
 - Adalimumab: 40 mg fortnightly
 - Golimumab: 50 mg monthly
 - Certolizumab pegol: 400 mg SC initially and at Weeks 2 and 4, followed by 200 mg every 2 weeks or 400 mg every 4 weeks

OR

• Recurrence of symptoms during scheduled maintenance dosing following prior clinical benefit (discontinuation despite clinical benefit does not qualify).

OR

• History of intolerance of at least one TNF antagonist (including, but not limited to infusion-related reaction, demyelination, congestive heart failure and infection).

5.2 Exclusion Criteria

Subjects are excluded from the study if any of the following criteria apply:

- 1. A current diagnosis of axSpA with a BASDAI >4 but no evidence of inflammation on MRI.
- 2. Discontinued biologic therapy such as adalimumab, etanercept, infliximab, golimumab and certolizumab pegol <8 weeks prior to Baseline.
- 3. Previous or current use of oral corticosteroid and meets one of the following criteria:
 - Is receiving prednisone or prednisone equivalent >10 mg/day at Baseline;
 - Has discontinued use of corticosteroid within 28 days of Baseline;
 - Has not been on stable doses of corticosteroid for at least 28 days prior to Baseline; or
 - Has been taking both oral budesonide and prednisone (or equivalent) simultaneously.
- 4. Received intra-articular corticosteroids during the Screening Period or i.v. corticosteroids within 14 days prior to Screening or during the Screening Period.
- 5. Received anti-IL-17A or anti IL12/23 therapy.
- 6. Received cyclosporine, tacrolimus or mycophenolate mofetil within 28 days prior to Baseline.
- 7. Previously received stem cell transplantation.
- 8. Infection(s) requiring treatment with i.v. anti-infectives within 28 days prior to the Baseline Visit or oral anti-infectives within 14 days prior to the Baseline Visit.
- 9. Screening laboratory and other analyses show any of the following abnormal results:

- Bilirubin > upper limit of normal (ULN) and serum AST or $ALT > 1.5 \times ULN$;
- Estimated glomerular filtration rate <40 mL/min/1.73 m²;
- Total white blood cell (WBC) count $<3,000/\mu$ L;
- Absolute neutrophil count (ANC) $< 1,000/\mu$ L;
- Platelet count $<100,000/\mu$ L;
- Absolute lymphocyte count <750/µL;
- Haemoglobin <9 g/dL.
- 10. Any active or recurrent viral infection that based on the Investigator's clinical assessment makes the subject an unsuitable candidate for the study, including recurrent/disseminated herpes zoster or known history of human immunodeficiency virus (HIV).
- 11. Hepatitis B (hepatitis B virus surface antigen [HBsAg] positive [+] or detected sensitivity on the hepatitis B virus [HBV] DNA polymerase chain reaction [PCR] qualitative test for hepatitis B core antibodies [HBc Ab]/hepatitis B surface antibody [HBsAb] positive subjects) or hepatitis C (hepatitis C virus [HCV] RNA detectable in any subject with anti-hepatitis C virus antibody [HCV Ab]).
- 12. Any active or chronic recurring infections or untreated latent TB.
- 13. History of moderate-to-severe congestive heart failure (New York Heart Association [NYHA] class III or IV), risk factors for coronary syndrome, hypertension, angina and myocardial infarction, cerebrovascular accident and any other condition within 6 months, which in the opinion of the Investigator, would put the subject at risk by participation in the study.
- 14. Receipt of any live vaccine within 2 weeks prior to randomisation, or will require live vaccination during study participation including up to 1 month after the last dose of study drug.
- 15. Evidence of current or prior dysplasia or history of malignancy (including of the gastrointestinal tract) other than a successfully treated non-metastatic cutaneous squamous cell or basal cell carcinoma or localised carcinoma in situ of the cervix or adenomatous polyp that has been completely resected.
- 16. Has had any uncontrolled and/or clinically significant (per Investigator's judgement) illness, hospitalisation, or has had any surgical procedure requiring general anaesthesia within 30 days prior to Screening, or has any planned surgical procedure within 6 months after randomisation.
- 17. Known current or previous interstitial lung disease.
- 18. Positive pregnancy test at Screening (serum) or Baseline (urine).
- 19. Female subjects who are breastfeeding or considering becoming pregnant during the study.
- 20. Considered by the Investigator, for any reason, to be an unsuitable candidate for the study.
- 21. Received any investigational agent or procedure within 30 days or 5 half-lives prior to Baseline, whichever is longer.

- 22. History of clinically significant drug or alcohol (> 40 units per week) use in the last 12 months.
- 23. Related to or a dependent of the site staff, or a member of the site staff.

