AE=adverse event; ANA=anti-nuclear antibody; ASDAS=Assessment of SpondyloArthritis Disease Activity Score; BASDAI=Bath Ankylosing Spondylitis Disease Activity Index; BASFI=Bath Ankylosing Spondylitis Functional Index; CRP=C-reactive protein; ECG=electrocardiogram; EoT=End of Treatment; ESR=erythrocyte sedimentation rate; ET=Early Termination; FU=Follow-up; GM-CSF=granulocyte-macrophage colony-stimulating factor; Hep=hepatitis; HIV=human immunodeficiency virus; IMP=investigational medicinal product; MRC=Medical Research Council; MRI=magnetic resonance imaging; PAP=pulmonary alveolar proteinosis; PD=pharmacodynamic; PK=pharmacokinetic; WOCBP=women of childbearing potential.

- 1. Screening may be a maximum 4 weeks prior to baseline for some subjects (where stabilisation/wash-out of concomitant medication is needed) and only 1 week prior to baseline for subjects that already meet all inclusion/exclusion criteria).
- 2. Subjects who discontinue the study prior to the EoT visit should attend the EoT/ET visit and follow the schedule for the FU period.
- 3. One FU telephone contact will be performed between study completion and end of study visit approximately 6 weeks after last dosing; AE and concomitant medication will be collected.
- 4. In the treatment period, both pre-dosing and post-dosing (approximately 30 minutes post-dosing) vital sign assessments are to be performed.
- 5. Blood draw for evaluation of CRP and ESR only.
- 6. Pregnancy testing at Screening will be in serum; pregnancy testing at other visits will be in urine; a positive urine test will be confirmed with a serum pregnancy test.
- 7. Lung function tests includes: FEV₁, FVC and PEF.
- 8. Chest x-ray within 3 months of Screening to assess for PAP.
- 9. The pre-dosing MRI can be performed within 6 months before Screening.
- 10. Although the post-dosing EoT MRI is scheduled to occur at the week 12 visit, the MRI may be performed between weeks 12 and 16 if possible for study centres with logistical issues that prevent performing the MRI at the week 12 visit. The EoT MRI is optional; however, the study centres are requested to perform the EoT MRI on all subjects to the extent possible.
- 11.PK/PD sampling must be taken pre-dose (t=0).
- 12. Stored sample for immunogenicity assessment for evaluation of anti-namilumab antibodies.
- 13.Immunology assessment for evaluation of ANA (anti-dsDNA if ANA is positive).
- 14.HLA-B27 testing will only be performed in subjects whose HLA-B27 status is unknown.

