2.3 Benefit/Risk Assessment

Namilumab has not yet been administered to patients with axSpA, and therefore no benefit has yet been shown.

Namilumab has been administered to healthy volunteers, subjects with psoriasis and subjects with RA. However, due to limited clinical experience with namilumab, all subjects should be closely monitored for any potential occurrence of serious events, such as severe hypersensitivity or lung disorders, cardiac events and hepatic toxicity. When necessary, namilumab administration should be discontinued and appropriate medical interventions initiated. In addition, appropriate prophylactic measures should also be considered in subjects thought to be at higher risk for these events.

The possibility of a severe allergic reaction, including anaphylaxis, which can manifest as lifethreatening bronchospasm or hypotension, should always be considered. A physician should be available on-site and supplies of epinephrine, antihistamine and corticosteroid readily accessible when a subject is being administered the investigational medicinal product (IMP). A subject who has such an allergic reaction should not receive additional IMP injections.

Special attention should be given to respiratory symptoms arising during namilumab treatment, due to the theoretical risk of pulmonary alveolar proteinosis (PAP). If the symptoms are mild and a likely cause of the symptoms can be established, the subject can remain in the study and the condition treated at the discretion of the Investigator. Should the symptoms be severe, or no likely cause can be established, the subject should be referred to a pulmonologist for further evaluation that may include chest computer tomography scanning and broncho-alveolar lavage including cytology.

In case of unforeseen (e.g., dental) surgery between Screening and End of Study, subjects should receive adequate antibiotic prophylaxis.

Clinical evidence indicates that immunisation in subjects with immune-mediated inflammatory diseases does not increase clinical or laboratory parameters of disease activity (Gluck 2008). Live vaccines are contraindicated because of the potential risk of immune-suppression associated with any immunomodulators, but non-live (killed) vaccines can be used (Rahier 2010). Vaccination status is best checked and updated before the start of any immunomodulatory therapy with agents such as MTX or namilumab.

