7.0 DISCONTINUATION OF STUDY TREATMENT AND SUBJECT DISCONTINUATION/WITHDRAWAL

7.1 Discontinuation of Study Treatment

Subjects may be discontinued from study treatment for the following reasons:

- 1. Pre-treatment event or treatment-emergent AE. The subject has experienced a pre-treatment event or a treatment-emergent AE that requires early termination because continued participation imposes an unacceptable risk to the subject's health or the subject is unwilling to continue because of the pre-treatment event or AE.
 - Liver Function Test Abnormalities
 - Study medication must be discontinued immediately with appropriate clinical follow-up (including repeat laboratory tests) until the subject's laboratory profile has returned to normal/baseline status, if the following circumstances occur at any time during study medication treatment:
 - ALT or AST $> 8 \times$ ULN, or
 - ALT or AST $>5 \times$ ULN and persists for more than 2 weeks, or
 - ALT or AST >3 × ULN in conjunction with elevated total bilirubin >2 × ULN or international normalised ratio (INR) >1.5, without any anti-coagulant treatment, or
 - ALT or AST >3 × ULN with appearance of fatigue, nausea, vomiting, right upper quadrant pain or tenderness, fever, rash and/or eosinophilia (>5%).
- 2. If a diagnosis of PAP is confirmed during the course of this study (see Section 8.2.4), the subject should be withdrawn and treatment initiated as applicable.
- 3. Major protocol deviation. The discovery post-randomisation that the subject failed to meet protocol entry criteria or did not adhere to protocol requirements, and continued participation poses an unacceptable risk to the subject's health.
- 4. Lost to follow-up. The subject did not return to the clinic and attempts to contact the subject were unsuccessful. Attempts to contact the subject must be documented.
- 5. Pregnancy. The subject is found to be pregnant.

Subjects who discontinue study treatment will not be replaced.

See the SoA for data to be collected at the time of treatment discontinuation and follow-up and for any further evaluations that need to be completed.

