Appendix 8 Protocol Amendment History

The Protocol Amendment Summary of Changes Table for the current amendment is located directly before the Table of Contents (TOC).

Amendment 1 (04 May 2018)

This amendment is considered to be substantial based on the criteria set forth in Article 10(a) of Directive 2001/20/EC of the European Parliament and the Council of the European Union.

Overall Rationale for the Amendment 1:

The protocol was amended to address findings from a review by the Medicines and Healthcare Products Regulatory Agency (MHRA), which included clarifying several safety assessment time periods, revising an exclusion criterion based on abnormal liver transaminases, clarifying the process for the investigator to unblind study treatment in the event of a medical emergency, clarifying documentation of pulmonary alveolar proteinosis assessments, revising pregnancy contraception for consistency with Clinical Trial Facilitation Group (CTFG) guidance, and clarifying several inconsistencies.

Section #	Description of Change	Brief Rationale
1.3/Table 1/Footnote 4	Time period for post-dosing vital signs added.	Time period for post-dosing vital signs clarified per request from MHRA.
1.3/Table 1/Footnote 8	Changed chest x-ray timing from 6 months to 3 months.	Revised for consistency with body of protocol.
5.2/Exclusion criterion #9	Exclusion based on abnormal liver transaminases revised.	Criterion revised to exclude subjects with elevated transaminases who also have elevated bilirubin.
6.2.1, 6.3.1, 6.3.3, 6.3.4, 6.3.5	Text revised to include interactive web response system (IWRS) for maintaining treatment blind that will allow investigators to unblind a subject's investigational medicinal product identity at any time in the event of a medical emergency.	Process for unblinding of subject's investigational medicinal product by investigator in the event of a medical emergency clarified.
8.2.5	Documentation of pulmonary alveolar proteinosis assessments revised.	Documentation of pulmonary alveolar proteinosis assessments revised and clarified to include all assessments.
Appendix 6	Events where referral to a pulmonologist is required were updated.	Revisions were made for consistency with Section 8.2.5 of the protocol body.
Appendix 7	Barrier methods for pregnancy contraception deleted and acceptable contraception revised.	Methods of pregnancy contraception revised to be consistent with CTFG recommendations.

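### Exclusion criterion 9 sets no ALT or AST limit when bilirubin is normal, so a subject can be randomised and dosed above the 8 × ULN level at which Section 7.1 requires study drug to stop

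*Protocol*

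**What the plan says.** Entry. Protocol Section 5.2, criterion 9, applies when "Screening laboratory and other analyses show any of the following abnormal results". Its liver item reads "Bilirubin > upper limit of normal (ULN) and serum AST or" ALT above 1.5 × ULN. The other items in the same criterion are stand-alone numeric limits: eGFR, white cells, neutrophils, platelets, lymphocytes and haemoglobin. No other inclusion or exclusion criterion gives a number for ALT or AST.

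Intent. Appendix 8 says that Amendment 1 responded to a review by the UK regulator and that the liver item was changed as part of it. The recorded reason is "Criterion revised to exclude subjects with elevated transaminases who also have elevated bilirubin".

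Stopping. Protocol Section 7.1, under liver function test abnormalities, says "Study medication must be discontinued immediately with appropriate clinical follow-up", and that this holds "if the following circumstances occur at any time during study medication treatment". The circumstances are:

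- ALT or AST >8 × ULN, with no other condition;
- ALT or AST >5 × ULN lasting more than 2 weeks;
- ALT or AST >3 × ULN together with total bilirubin >2 × ULN, or with INR >1.5 off anticoagulants;
- ALT or AST >3 × ULN when listed symptoms or eosinophilia appear.

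Context. Section 2.3 asks that all subjects be "closely monitored for any potential occurrence of serious events, such as severe hypersensitivity or lung disorders, cardiac events and hepatic toxicity". Inclusion criterion 9 allows stable methotrexate or leflunomide.

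**The concern.** An entry rule and a stopping rule on the same laboratory test should fit together: a value that ends treatment at once should not be acceptable on the day treatment starts. Here the entry rule acts only when bilirubin is raised, while the strictest stopping rule ignores bilirubin. An isolated transaminase rise therefore falls between the two.

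The stake is patient safety in the first use of namilumab in axial spondyloarthritis, in a protocol that itself lists hepatic toxicity among the events to watch for. There is also a practical problem for sites. Following Section 5.2 to the letter can lead directly to a subject for whom Section 7.1 requires study drug to be stopped.

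**Working it through.** There is no planned figure to reproduce. The check sets the two rules against each other, in multiples of ULN, with b for bilirubin and m for the larger of AST and ALT.

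1. Criterion 9 as written excludes if b > 1 and m > 1.5. If b ≤ 1, the first part fails and no value of m excludes.

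2. Section 7.1, with its third circumstance split in two, gives five routes to an immediate stop. For each, ask whether a subject who passes criterion 9 could meet it.

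| Section 7.1 route | Can a subject who passes criterion 9 meet it? | Further condition needed |
|---|---|---|
| m > 8 | Yes, if b ≤ 1 | None |
| m > 5 | Yes, if b ≤ 1 | Persists more than 2 weeks |
| m > 3 and INR > 1.5 | Yes, if b ≤ 1 | INR > 1.5, no anticoagulant |
| m > 3 with symptoms or eosinophilia | Yes, if b ≤ 1 | Their appearance |
| m > 3 and b > 2 | No | Not applicable |

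The last row follows directly: b > 2 implies b > 1, and m > 3 implies m > 1.5, so criterion 9 already excludes.

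3. Worked case for the first row: b = 0.8, ALT = 9. Criterion 9 asks for 0.8 > 1, which is false, so the subject is not excluded. Section 7.1 asks for 9 > 8, which is true, so study medication must stop if that value is present on treatment.

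4. Does the result depend on how the liver item is parsed? Three readings were run over a grid of b = 0.8, 1.0, 1.2 and 2.5, AST and ALT each 1, 2, 4, 6 and 9, and persistence, INR > 1.5 and symptoms each present or absent.

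- Bilirubin and (AST or ALT): the first four routes are reachable and the fifth is not.
- (Bilirubin and AST) or ALT: the same four routes stay reachable, through isolated AST only. AST = 9 with ALT = 1 and b = 0.8 still passes.
- Any one of the three alone: no route is reachable. This reading conflicts with the word *and* and with the reason recorded in Appendix 8.

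The first reading is the one that the documents support. The grid shows which combinations are possible; it says nothing about how often they occur.

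5. Other criteria. Criteria 13 (other conditions within 6 months that put the subject at risk), 16 (uncontrolled or clinically significant illness) and 20 (unsuitable for any reason) could each keep such a subject out. All three rest on the investigator's judgement and none names a transaminase level.

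**The case against.** The strongest reply is that the two rules govern different times. Criterion 9 concerns screening results; Section 7.1 concerns treatment. Each can be obeyed as written, so this is a gap rather than a contradiction in wording. That is fair, and a raised screening value may settle before dosing. But the criteria do not require that to be shown, so the gap remains.

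The joint condition is also deliberate and came out of a regulator's review. That settles what criterion 9 means. It does not explain how the criterion fits with Section 7.1, and neither document discusses the fit.

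Investigators would probably decline such a subject under criterion 13, 16 or 20. They may, but the protocol chose hard limits for every other laboratory item in criterion 9.

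A reader might infer more than the documents support:

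- That every Section 7.1 level is open at entry. Only >8 × ULN is open without a further condition. For the symptom route, the wording about appearance suggests new onset, and Section 2.2 lists fatigue as a feature of the disease.
- That a known high value would go unfollowed, because full chemistry is scheduled only at Screening and Weeks 0, 6 and 12. Section 8.2.8 calls for clinically significant abnormal values to be repeated until they resolve or cease to matter, and Section 8.0 allows unscheduled safety samples.
- That the efficacy result or the adverse event tables would be distorted. SAP Section 14.1.2 ties non-response to missing Baseline or Week 12 data, not to stopping drug. Protocol Section 9.4.2 counts only events that first occur or worsen after the first dose. Section 8.2.7 records clinically significant screening abnormalities as concurrent conditions.
- That namilumab has a demonstrated liver problem at this dose. Section 4.3 mentions raised liver tests among single cases and reports no serious or clinically significant ones.

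**Conclusion.** The point holds in a limited form. With bilirubin at or below ULN, no numeric limit on ALT or AST applies at entry, and a subject above 8 × ULN can be correctly randomised and dosed although Section 7.1 requires an immediate stop at that level during treatment. Of the five stopping routes, one overlaps with eligibility unconditionally, three overlap conditionally, and one is already closed by criterion 9.

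This rests on two assumptions: that criterion 9 is read as joint, which Appendix 8 supports, and that the raised value is still present once dosing begins. The number of subjects affected cannot be derived, since neither document gives a distribution of screening transaminases. The ground is safety and internal consistency; the documents do not support treating it as a threat to the primary analysis. It should be corrected because it is specific and cheap to correct.

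**What to change.** The sponsor's medical team should reconcile the liver item of Section 5.2, criterion 9, with the liver stopping limits in Section 7.1, so that the entry and stopping rules are consistent, and should record the reasoning. Which levels apply is a clinical decision for that team; no threshold or clinical rule is proposed here.

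The cost is a short protocol amendment and notice to sites. Screening chemistry is already scheduled, and the SAP analyses need no change. Depending on how the passages are reconciled, there may be a few more screen failures; the plan already allows for about 70 − 42 = 28 screened subjects who are not randomised. The main downside is that a criterion revised in Amendment 1 after regulator review is reopened.
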